## POSITIVE CONTROLS

Sufficient biting pressure (i.e., mosquito landing rates of at least 5 landings in 60 seconds in a 250 cm^2 area on an exposed untreated control arm) will be confirmed at the commencement of the study and throughout the study at the beginning of each exposure period. A positive control is intentionally excluded from the proposed study protocol for several reasons. Data on a positive control group serves no purpose in this study to confirm the mosquito repellency of the test product and determine

a reliable protection period under laboratory conditions. Putting additional subjects at risk, however minimal, to include a positive control group is not necessary.

### **SUPPORT STAFF**

Additional ICR staff members will support the Study Director and test subjects in their activities. These ICR staff members, along with the study director, will record all test data. Test subjects will not record any data. The study results would be difficult to defend in an EPA audit or in a court of law if a test subject records data.

### **MISCELLANEOUS**

Syringe, (minus the needle), micropipette and tips, Q-tip®s, latex or vinyl gloves, clip boards, data record forms, scissors, elastic bandages, Elastikon® tape, pencils, marking pens (e.g. Sharpie®), hygromograph, unscented Neutrogena® soap, paper towels and a stop watch.

### **RECORDS TO BE MAINTAINED**

All study notes, data collection sheets (true copies), SOPs (originals), Chain of Custody letters (true copies), Sample Log and Sample Record of Use Forms (true copies), the protocol (true copy) and signed Informed Consent documents will be maintained in the ICR archives. Original documents will be provided to the sponsor for archiving with the exception of SOPs, Master Schedules, signed Informed Consent documents, test article characterization, and personnel files.

### **RISK CHARACTERIZATION AND MINIMIZATION**

The subjects will be exposed to three types of risk:

1. Test articles.

The active ingredient, Picaridin® demonstrates a low acute oral, dermal and inhalation toxicity. It is classed as Category IV for acute inhalation toxicity and primary dermal irritation. It is not a dermal sensitizer. The EPA "New Pesticide Fact Sheet" indicates that the toxicology data base for the active ingredient is complete and no additional studies are required.

There is minimal risk for subjects to experience an adverse reaction to the insect repellents being tested. The study sponsor that developed the test materials has over 120 years of experience

formulating and producing a wide variety of cosmetics with worldwide sales. This company is strongly protective of its reputation, which it knowingly stakes on every product that it puts into commerce; that is, extreme care is taken in the development and production of safe and reliable products that are intended for direct application to the skin.

The test articles are an extension of a well known and highly regarded product line of bath and body products for skin smoothing and skin care that has evolved to include insect repellents. These proposed insect repellents use the active ingredient, Picaridin®, which was first registered by the US EPA under FIFRA on December 7, 2000. As required under FIFRA, registration of Picaridin® as an active ingredient is supported by an extensive data package that includes toxicity test data that demonstrate low acute and chronic toxicity. This active ingredient has been successfully used without significant incident by the study sponsor and other insect repellent formulators (and millions of consumers). All of the inert ingredients used in the finished insect repellent products have a long history of safe use in various cosmetics. The sponsor has used these ingredients safely in numerous cosmetic products applied directly to the skin.

Insect repellents that are part of this product line of bath and body products use one of three active ingredients, including Picaridin®. The sponsor's first insect repellent in this product line was first registered in 1997 and their first insect repellent utilizing Picaridin® was registered in 2005. The inert ingredients in the formulation were selected because they are widely used in cosmetic formulations, and are non-sensitizers. To expedite product registration under FIFRA, the sponsor has confirmed that the inert ingredients have been previously reviewed and approved by EPA for use in FIFRA registered products.

While there is low concern for the toxicity potential for the test samples to induce an adverse reaction in the test subjects, they will be monitored throughout the study and prompt medical attention will be obtained if any adverse reaction is observed among the subjects on test. Those individuals who are known to have allergies to mosquito bites, insect repellents, or skin care products will be excluded from participation in the study.

## 2. Bites from target mosquitoes.

The typical reaction to a bite from a mosquito can vary from person to person. Most people will experience a small area of redness, swelling and itching that usually goes away within 24 hours. In more sensitive individuals, the area of swelling and itching can be much larger and last for several days. In extremely rare cases, a serious reaction to a bite results in swelling of the throat, hives and wheezing. This condition (anaphylaxis) could be life-threatening and requires immediate medical attention.

All subjects known to have severe reactions to mosquito bites will be excluded from this study.

All subjects will be issued latex or vinyl gloves. Only a small portion (250 cm^2) of bare skin on each arm will be exposed. All other parts of the body will be covered with the subject's personal clothing. Immediately upon receiving a FCB on an arm, that arm will be withdrawn from the test and not be exposed to the caged mosquitoes again. Caladryl® or Calamine® lotion and rubbing alcohol will be available for use to mitigate any reaction to mosquito bites.

There will be First Aid qualified staff members on site, and First Aid supplies will be available at the test site at all times. A selected local hospital will receive prior notification of this study and on-site staff will have cell phones to make emergency calls if necessary. In the case of medical emergency, people will be transported to the selected local hospital, St. Agnes Hospital, by either ICR staff or professional ambulance. The hospital is 7 miles from the laboratory and is located at [name], Baltimore, MD. 21229. The telephone number is [contact]. If any test subjects need medical attention, their medical care will be paid by ICR.

### 3. Arthropod-borne diseases

There will be no risk for arthropod-borne diseases. The mosquitoes being used in this test are commonly called the southern house mosquito, which is one of the most common species throughout the southeastern United States, ranging as far north as the District of Columbia, and west to Missouri, Utah, New Mexico and California. This species can carry the West Nile virus, St. Louis encephalitis, and both Western and Venezuelan equine encephalitis.

This strain of mosquito has been laboratory colonized for many years and has not been exposed to outside blood sources. None of the mosquitoes used in this test will have had a blood meal prior to their introduction into the test cages. All mosquitoes used in the study will be destroyed either through starvation, freezing or exposure to carbon dioxide. Once a group of mosquitoes has been used in a study, it will not be re-used in another study. Therefore, transmission of a blood borne disease by these mosquitoes is not possible.

All of the above factors combined will minimize disease and bite risks. Also the subjects will only need to receive two bites within 30 minutes to confirm breakdown, after which the test arm will not be exposed to the mosquitoes again.

### **DISCOMFORT AND HAZARD**

Although the mosquitoes being used in this test are capable of transmitting the diseases listed above, in the wild, this strain of mosquito has been laboratory colonized for many years and has

not been exposed to outside blood sources. None of the mosquitoes used in this test will have had a blood meal prior to their introduction into the test cages. All mosquitoes used in the study will be destroyed either through starvation, freezing. Once a group of mosquitoes has been used in a study, it will not be re-used in another study. Transmission of a blood borne disease by these strains of mosquitoes is not possible.

In the event that study related injury or illness should occur, test subjects would be instructed to seek medical attention through a health care provider, at ICR's expense. Test subjects would be instructed to submit study related bills to ICR. ICR will incur the cost of any study related bills. The principle investigator will contact all test subjects by telephone, two weeks after the conclusion of the study to enquire if they have experienced any adverse effects.

### BENEFITS

While the sponsor gains the most direct benefit from the conduction of this study through knowledge gained on the performance of its repellent products, ICR and the sponsor also acknowledge that greater benefits exist to society at large. Insects continue to have a substantial impact on outdoor activities of many people. As the EPA registration requires efficacy data, the protocol in discussion is the only path toward development of alternative and perhaps more effective insect repellent products. Societal benefits from additional repellents becoming available in the market place would include:

1. New novel insect repellent formulas demonstrating increased effectiveness against mosquitoes would be available to consumers.
2. New repellent products would allow more choices to consumers.
3. New repellent products containing a DEET-alternative active ingredient would allow consumers a choice between DEET and non DEET repellent products.

### TEST SUBJECTS

**Inclusion Criteria:**

Sex: Male/Female  
Age: 18 to 55  
Race: No exclusions  
Literacy: Must be able to read, speak, and understand English

**Exclusion Criteria:**

1. Test subjects can not participate if they are pregnant or breastfeeding.
2. Test subjects can not be an employee or a relative of an employee of ICR Inc., the sponsor, or any interested party.
3. Test subjects must follow the requirements of the study as explained to them.
4. Test subjects must not be sensitive to mosquito bites.
5. Test subjects must have no known sensitivity to insect repellents or skin care products.
6. Test subjects must be attractive to mosquitoes, as evidenced by previous being bitten by mosquitoes.
7. Test subjects must not smoke or drink alcoholic beverages 12 hours prior to the test.
8. Test subjects must not use perfumed cosmetics, skin creams, shaving lotions, etc. after 12 AM before the test, and during the test.
9. Test subjects must wear proper protective clothing during the test, such as their own blue jeans, heavy socks, long sleeve shirts, and gloves provided by ICR.

*Number of Subjects and Rationale for Sample Size*

The EPA Guideline (EPA/OPPTS Guideline 810.3700) recommends at least six test subjects be used. Because of the cost of doing repellent studies, it is prudent to ensure data collected will give a good representation of the repellency of the test formulations. In a published paper the number of subjects required to achieve an estimated among-subjects standard deviation for specific times of 0.5 hours to 2.0 hours was calculated for protection times from 1 hour to 8 hours. The number of subjects required to achieve an estimated among-subjects standard deviation of 2.0 hours at a 95% confidence level for an 8 hour protection time was calculated to be between 10 and 11 subjects. This study, therefore, will use ten treated test subjects. There will be an additional control subject, plus two additional treated test subjects to replace anyone that either drops out or is ineligible to participate due to a positive pregnancy test or other unforeseen circumstances. These additional two treated test subjects will help to ensure a minimum "n" of ten and will aid in protecting the privacy of any dropouts.

---

 L.C. Rutledge and R. K. Gupta, 1999, Variation in The Protection Periods of Repellents on Individual Human Subjects: An Analytical Review, Journal of the American Mosquito Control Association, 15(3):348-355

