### HYPOTHESIS

The repellent samples are expected to provide 8 hours of personal protection from *Culex quinquefasciatus* mosquitoes, a West Nile virus vectors, in the laboratory.

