### OBJECTIVE

The objective of the study is to determine the mean protection time from bites provided by the test articles under laboratory conditions to confirm the hypothesis. Therefore ICR will conduct a laboratory study to assess repellency of these test articles against *Culex quinquefasciatus* mosquitoes.

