## **METHODS**

### *Experimental Design*

This is a subject-blinded study. The delineated areas on the arms of subjects will be treated and used as test areas. Only arms are being treated in this study, since arms are quite easy to monitor for mosquito activity. Therefore there will be twelve test arms for each treatment. Each test

subject will have one arm treated with one of the two test products and the other arm will be treated with the other test product.

*Test location:*

This test will be conducted in the insectary at ICR. The insectary is maintained at 70% RH  $\pm$  15% RH and 70° F  $\pm$  15°F.

*Dose*

The Standard application rate of 1.67 mg/cm^2 for this study. This is the dose currently recommended in the EPA guidelines for mosquito efficacy testing and the dose that was used when the efficacy field tests were conducted on these two EPA registered products.

*Blinding of the Study*

The test articles will be coded as "A" and "B". During the test these codes will be the only test article designation referred to or that the test subjects will see. The Study Director and members of the ICR staff will know the actual test articles, but will refrain from such identifications in the presence of test subjects.

*Treatment Groups*

There will be two groups: a treated group of twelve (two more than required to allow for drop outs) subjects whose arms will be treated, and one untreated (control) test subject whose arms will be untreated. Subjects will be given a subject number. They will be assigned to the groups by lottery selection of the subject number.

*Personnel preparation*

All test subjects will complete and will sign an "Informed Consent Document" prior to acceptance as a test participant.

Females will be required to perform an over the counter pregnancy test that will be supplied by ICR. They will do this the morning of the test. The results will be verified by a female ICR staff member. They may not participate if they are pregnant or breastfeeding. The results of this pregnancy test will be kept confidential and will not be disclosed to anyone other than the test subject and the P. I.

All test subjects will wash their arms with unscented Neutrogena® soap. The test subject's arms will then be measured in the following manner for the demarcation of the 250 cm^2 test area:

*For Arms:*

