### **DATA ANALYSIS:**

The purpose of this study is to examine the effective duration of an insect repellent. Ideally, it is expected that there will be no significant breakdown in efficacy of the product over a 8 hour interval. Given the small sample size ( $N = 10$ ) and the dichotomous nature of the data (effective vs. non-effective), nonparametric statistics will be used to analyze the data. Data will be analyzed using SPSS for Windows version 12.

Subjects will be evaluated each half hour over the 8 hour window of the study to determine whether or not the product continued to prevent insect bites. For each 30 minute assessment interval, the proportion of subjects not having insect bites will be identified. A basic degradation curve can then be plotted. These data will then be subjected to a Cochran Q test, which is particularly useful for measuring changes in frequencies (proportions) across time. A significant effect would indicate that there was a systematic degradation in the product's efficacy over the 8 hour testing interval. If such an effect is found with the Q test, then a series of 2 (baseline vs. assessment interval) X 2 (protected vs. non-protected) cross-tabulations will be created and the resulting proportions will be analyzed using a Fischer's Exact Test (employing a 1-tailed alpha level) to determine the specific time point at which efficacy became significantly impaired.

Data also to be collected from subjects will be the length of time before a significant number of bites were noted. These data will be aggregated and basic descriptive statistics determined (e.g., mean, standard deviation, confidence intervals). If this distribution is non-normal, appropriate transformations will be applied and statistics recalculated. In the case of negative skewness (which is expected), the data will be reflected and a logarithmic transformation will be employed. In the case of significantly skewed distributions, the median will be used as the measure of central tendency. Confidence intervals will be calculated on the basis of percentile ranks rather than standardized scores.

QAU AND DATA ARCHIVING

Good Laboratory Practices, as outlined in 40 CFR §160 will be followed throughout the study. The QAU representative will observe and write phase report(s) for this study. All data will be archived.

SCHEDULE OF EVENTS

DATE	PROCEDURE
Time Zero	Test Conducted
At End of Test	Verbal Report
After The Laboratory Test Conduct	Written Report

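### Ten subjects are justified on protection time in hours, but the only significance tests concern the proportion of arms protected, and a non-significant result would not support 8 hours of protection

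*Protocol*

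**What the plan says.** HYPOTHESIS: "The repellent samples are expected to provide 8 hours of personal protection". OBJECTIVE: the study is "to determine the mean protection time from bites provided by the test articles under laboratory conditions to confirm the hypothesis".

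The section Number of Subjects and Rationale for Sample Size reports, from a published paper, that "the number of subjects required to achieve an estimated among-subjects standard deviation for specific times of 0.5 hours to 2.0 hours was calculated", covering protection times of 1 to 8 hours. The case chosen is "an estimated among-subjects standard deviation of 2.0 hours at a 95% confidence level for an 8 hour protection time was calculated to be between 10" (the upper figure is 11), and the conclusion is: "This study, therefore, will use ten treated test subjects". No half-width, power or proportion is given. Treatment Groups then has "a treated group of twelve (two more than required to allow for drop outs) subjects whose arms will be treated".

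DATA ANALYSIS moves to a yes/no outcome: "Given the small sample size ( $N = 10$ ) and the dichotomous nature of the data (effective vs. non-effective), nonparametric statistics will be used". The proportion of subjects without bites at each half hour goes into a Cochran Q test, read as follows: "A significant effect would indicate that there was a systematic degradation in the product's efficacy over the 8 hour testing interval". If Q is significant, one-tailed exact tests compare each interval with baseline. The alpha value is not stated. A final paragraph plans a mean, standard deviation and confidence interval for the time to failure, with the median and percentile-based intervals if the data are skewed.

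Under Testing and Criteria for Test End Point, exposure of an arm stops at the first confirmed bite or at 8 hours.

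**The concern.** The number of subjects is argued on one scale (hours) and significance is tested on another (proportion protected). OBJECTIVE points to the mean protection time, but no section gives a criterion for it or says which of the two analyses confirms the 8-hour hypothesis.

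The two questions differ. A product whose protection times centre on 8 h has about half its arms failing by then, so a proportion test will often report degradation. Conversely, with ten arms an absence of significance is compatible with several arms failing. STUDY RATIONALE says the data are meant to support a label claim, so a reader needs to know what a significant or a non-significant result says about 8 hours of protection. The protocol does not tell them.

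**Working it through.** **Inputs from the protocol.** 2.0 h, 95% confidence and 8 h (sample-size section); 10 subjects required and 12 treated, each with one arm per product; Cochran Q, then a one-tailed exact test against baseline (DATA ANALYSIS); observation to 8 h.

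**Assumptions, because the protocol is silent.** One-tailed alpha of 0.05, with 0.025 as a sensitivity; the distribution of latent protection times; failed arms stay counted as failed; all arms protected at baseline.

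**1. The plan's own figure.** For a mean, n = (1.96 × SD / E)², where E is the half-width. E is not stated, so 10 to 11 cannot be reproduced.
- With SD = 2.0 h: E = 1.0 gives 15.4, E = 1.2 gives 10.7, E = 1.25 gives 9.8 and E = 2.0 gives 3.8.
- If 2.0 h is instead the half-width, SD = 2.0 × √n / 1.96, which is 3.2 h for n = 10 and 3.4 h for n = 11.

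Neither reading involves a proportion.

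**2. When the exact test is significant.** With n of n protected at baseline and k failures later, the one-sided p is C(n,k) / C(2n,k).
- n = 10: k = 3 gives 120/1140 = 0.105; k = 4 gives 210/4845 = 0.043; k = 5 gives 252/15504 = 0.016.
- n = 12: k = 3 gives 220/2024 = 0.109; k = 4 gives 495/10626 = 0.047; k = 5 gives 792/42504 = 0.019.

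The threshold is 4 failures at 0.05 and 5 at 0.025, for either n.

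**3. Latent times centred on 8 h.** If times are symmetric about 8 h, each arm fails by 8 h with probability 0.5, whatever the SD.
- n = 10, alpha 0.05: 1 − (1 + 10 + 45 + 120)/1024 = 0.828.
- n = 10, alpha 0.025: 1 − 386/1024 = 0.623.
- n = 12, alpha 0.05: 1 − 299/4096 = 0.927.

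Requiring a significant Cochran Q first does not change this (simulated joint probability 0.829; 20,000 runs, normal, SD 2 h, n = 10).

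Sensitivity for n = 10, with mean 8 h, SD 2 h and failures counted up to the time shown:

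| Shape | Alpha 0.05: 8.0 h | 7.75 h | 7.5 h | Alpha 0.025: 8.0 h | 7.75 h | 7.5 h |
|---|---|---|---|---|---|---|
| Normal | 0.828 | 0.735 | 0.621 | 0.623 | 0.496 | 0.370 |
| Weibull | 0.801 | 0.704 | 0.591 | 0.583 | 0.459 | 0.341 |
| Gamma | 0.877 | 0.799 | 0.694 | 0.702 | 0.581 | 0.449 |
| Lognormal | 0.897 | 0.824 | 0.723 | 0.736 | 0.617 | 0.482 |

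The range is about 59–90% at 0.05 and 34–74% at 0.025.

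**4. What the recorded mean can show.** No recorded time exceeds 8 h, so the recorded mean equals 8 h only if essentially every arm lasts. For latent normal times with mean 8 h and SD 2 h, the expected recorded mean is 8 − 2 × 0.399 = 7.2 h (simulated SD 1.2 h).

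**5. The reverse direction.** At 0.05, 3 failures of 10 are not significant (p = 0.105). With 7 of 10 protected, the exact one-sided 95% lower bound solves Σ C(10,x) pˣ(1−p)¹⁰⁻ˣ = 0.05 over x = 7 to 10, giving p = 0.39. A result read as no significant breakdown is then compatible with well under half of arms being protected through 8 h.

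**6. Precision available from the existing subjects** (exact one-sided 95% lower bounds).
- 10/10: 0.05^(1/10) = 0.741.
- 9/10: 10p⁹ − 9p¹⁰ = 0.05 gives 0.606.
- 12/12: 0.05^(1/12) = 0.779.
- 11/12: 12p¹¹ − 11p¹² = 0.05 gives 0.661.

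**The case against.** The strongest reply has four parts.

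- **No pass/fail rule is written.** DATA ANALYSIS describes an expectation and how a significant Q would be read; it does not tie the tests to acceptance of the hypothesis. This stands. A reader might infer that the tests are a decision rule that rejects a product meeting the planning values, but the text does not say so.
- **An analysis on the hours scale is planned.** The mean and confidence interval match the OBJECTIVE and the scale of the sample-size argument, so it would be wrong to say that ten subjects support nothing in the analysis. This stands. What remains is that n was not derived for the significance tests and no one analysis is named as decisive.
- **The two analyses need not conflict.** Because times are capped at 8 h, four or more failures also pull the recorded mean below 8 h. With latent normal times (mean 8 h, SD 2 h) and n = 10, this happened in over 99.9% of simulated runs with four or more failures. Both results then point short of 8 h. They differ in strength: the two-sided 95% interval for the recorded mean excluded 8 h in only about 33–46% of all runs. A claim of opposite verdicts is therefore not supported.
- **Mean 8 h with SD 2.0 h is only one reading.** The text speaks of achieving an SD, and 2.0 h could be a precision. STUDY RATIONALE also reports earlier results up to and beyond 8 hours, so the true centre may be later. This limits the shape-dependent figures. It does not affect the symmetric result, which needs only a centre at 8 h, and it does not touch step 5.

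A statistical analysis plan might name the decisive analysis, but the sample-size argument and the tests are fixed in the protocol and do not correspond.

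**Conclusion.** The point holds as a mismatch between the sample-size argument and the significance tests, with no stated link from either planned analysis to the 8-hour hypothesis.

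Its size is conditional. If latent times centre on 8 h, the tests would be significant by 8 h about 83% of the time with ten arms at one-tailed 0.05 (59–90% across the shapes and cut-offs tried) and about 62% at 0.025 (34–74%). With twelve arms at 0.05 the symmetric figure is about 93%. A reader might take these as false-positive rates. They are not: in that scenario about half the arms truly fail, and the tests detect it.

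The firmer consequence is that non-significance is weak evidence. At an assumed one-tailed 0.05, up to three of ten arms can fail by 8 h without significant impairment, so absence of a significant result cannot stand as support for 8 hours of protection. The point is worth correcting before the study; it does not invalidate the design.

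**What to change.** 1. In DATA ANALYSIS, report for each product the number of treated arms with no confirmed bite through 8 h, with an exact (Clopper-Pearson) one-sided 95% lower bound. Base the 8-hour conclusion on that bound, not on whether Q or an exact test is significant. Keep those tests as supportive. Keep the protection-time summaries as planned, treating arms that last to 8 h as censored.
2. In Number of Subjects and Rationale for Sample Size, replace the claim to achieve an SD of 2.0 h with the precision of that statistic: lower bounds of 74% for 10/10, 61% for 9/10, 78% for 12/12 and 66% for 11/12.

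The OBJECTIVE on protection time can stay. The cost is wording in two sections and one exact interval per product, with no extra subjects or procedures. The drawback is that the stated precision will look less favourable than the present rationale suggests.
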